**Listing 11.4.1.2 Hematological abnormalities grade  $\geq 3$  by treatment**

Study Part	Sequence	Treatment Group*	Subject	Cycle	Event	Grade
...						
...						

\* ITZ+LRB / LRB

**Listing 11.4.1.3 Hematological tests not assessed by treatment**

Study Part	Sequence	Treatment Group*	Subject	Cycle	Lab. test
...					
...					

\* ITZ+LRB / LRB

**Table 11.4.1.4 Hematological abnormalities: Worst grade per patient**

	Part A			Part B			Part A+B			Total		
	S1 (TR)			S1 (TR)			S2 (RT)			S1 (TR)		
	All grades	Gr $\geq 3$	Gr $\geq 4$	All grades	Gr $\geq 3$	Gr $\geq 4$	All grades	Gr $\geq 3$	Gr $\geq 4$	All grades	Gr $\geq 3$	Gr $\geq 4$
	N	%	N	%	N	%	N	%	N	%	N	%
Anemia												
Leukopenia												
Lymphopenia												
Neutropenia												
Thrombocytopenia												

Notes: Percentage is based on number of patients by study part and sequence, when applicable.

Part A, patients assigned to Sequence 1; Part B, sequence assigned randomly.

S1, Sequence 1; S2, Sequence 2; TR, test-reference; RT, reference-test.

**Listing 11.4.1.5 Hematological abnormalities per patient grade  $\geq 3$**

Study Part	Sequence	Treatment Group*	Subject	Cycle	Event	Cycle	Grade
...							
...							

\* ITZ+LRB / LRB

**Listing 11.4.1.6 Hematological tests not assessed per patient**

Study Part	Sequence	Treatment Group*	Subject	Cycle	Lab. test
...					
...					

\* ITZ+LRB / LRB

## 11.4.2 Biochemical Abnormalities

Table 11.4.2.1 Biochemical abnormalities: Worst grade per treatment

Part A																			
T			R																
All grades		Gr ≥ 3	Gr ≥ 4		All grades		Gr ≥ 3	Gr ≥ 4		All grades									
N(%)		N(%)	N(%)		N(%)		N(%)	N(%)		N(%)									
ALT increase																			
AST increase																			
...*																			
Part B																			
S1						S2													
T			R			R			T										
All grades		Gr ≥ 3	Gr ≥ 4	All grades		Gr ≥ 3	Gr ≥ 4	All grades		Gr ≥ 3	Gr ≥ 4								
N(%)		N(%)	N(%)	N(%)		N(%)	N(%)	N(%)		N(%)	N(%)								
ALT increase																			
AST increase																			
...*																			
Part A+B (S1)																			
T						R													
All grades		Gr ≥ 3	Gr ≥ 4	All grades		Gr ≥ 3	Gr ≥ 4	All grades		Gr ≥ 3	Gr ≥ 4								
N(%)		N(%)	N(%)	N(%)		N(%)	N(%)	N(%)		N(%)	N(%)								
ALT increase																			
AST increase																			
...*																			

Notes: Percentage is based on number of patients by study part and sequence, when applicable.

\*Creatinine increased, hyperglycemia, hypoglycemia, CPK increased, GGT increased, bilirubin increased, hypoalbuminemia, hypernatremia, hyponatremia, hyperkalemia, hypokalemia, hypermagnesemia, hypomagnesemia, hypercalcemia, hypocalcemia.

Part A, patients assigned to Sequence 1; Part B, sequence assigned randomly.

S1, Sequence 1; S2, Sequence 2.

T, Test (ITZ+LRB); R, Reference (LRB alone).

Listing 11.4.2.2 Biochemical abnormalities grade ≥ 3 by treatment

Study Part	Sequence	Treatment Group*	Subject	Event	Grade
...					

\* ITZ+LRB / LRB

Listing 11.4.2.3 Biochemical tests not assessed by treatment

Study Part	Sequence	Treatment Group*	Subject	Lab. test
...				

\* ITZ+LRB / LRB

Table 11.4.2.4 Biochemical abnormalities: Worst grade per patientpatientpatientpatientpatient

	Part A						Part B						Part A+B						Total	
	S1 (TR)			S1 (TR)			S2 (RT)			S1 (TR)			S1 (TR)			S1 (TR)				
	All grades	Gr ≥ 3	Gr ≥ 4	All grades	Gr ≥ 3	Gr ≥ 4	All grades	Gr ≥ 3	Gr ≥ 4	All grades	Gr ≥ 3	Gr ≥ 4	All grades	Gr ≥ 3	Gr ≥ 4	All grades	Gr ≥ 3	Gr ≥ 4		
	N	%	N	%	N	%	N	%	N	%	N	%	N	%	N	%	N	%		
ALT increase																				
AST increase																				
...	*																			

Notes: Percentage is based on number of patients by study part and sequence, when applicable.

Part A, patients assigned to Sequence 1; Part B, sequence assigned randomly.

S1, Sequence 1; S2, Sequence 2; TR, test-reference; RT, reference-test.

Listing 11.4.2.5 Biochemical abnormalities per patientpatientpatientpatientpatient grade ≥ 3

Study Part	Sequence	Treatment Group*	Subject	Cycle	Event	Cycle	Grade
...							

\* ITZ+LRB / LRB

Listing 11.4.2.6 Biochemical tests not assessed per patientpatientpatientpatientpatient

Study Part	Sequence	Treatment Group*	Subject	Cycle	Lab. test
...					

\* ITZ+LRB / LRB

### 11.4.3 Laboratory Values Over Treatment

Table 11.4.3.1 Shift of hematological abnormalities, worst grade per patient vs. baseline

Baseline grade	Worst grade per patient during treatment									
	Grade 1		Grade 2		Grade 3		Grade 4		Grade 5	
	N	%	N	%	N	%	N	%	N	%
Part A - S1 (TR)										
Anemia	G0									
	...									
	G4									
Leukopenia	G0									
	...									
	G4									
...	G0									
	...									
	G4									
Part B - S1 (TR)										
Anemia	G0									
	...									
	G4									
Leukopenia	G0									
	...									
	G4									
...	G0									
	...									
	G4									
Part B - S2 (RT)										
Anemia	G0									
	...									
	G4									
Leukopenia	G0									
	...									
	G4									
...	G0									
	...									
	G4									

Notes: Percentage is based on number of patients by study part and sequence, when applicable.

Part A, patients assigned to Sequence 1; Part B, sequence assigned randomly.

S1, Sequence 1; S2, Sequence 2; TR, test-reference; RT, reference-test.

If a low number of patients with grade  $\geq 3$  neutropenia or thrombocytopenia, the following table will be omitted and the information will be provided in a listing.

Table 11.4.3.2 Time course for neutrophils and platelets

	Part A		Part B		Part A+B		Total	
	S1 (TR)		S1 (TR)		S2 (RT)			
	N	Median (range)	N	Median (range)	N	Median (range)		
Neutropenia (Grade $\geq 3$ )								
Onset day								
Nadir day								
Recovery day								
Days to recovery								
Thrombocytopenia (Grade $\geq 3$ )								
Onset day								
Nadir day								
Recovery day								
Days to recovery								

Part A, patients assigned to Sequence 1; Part B, sequence assigned randomly.

S1, Sequence 1; S2, Sequence 2; TR, test-reference; RT, reference-test.

Table 11.4.3.3 Shift of biochemical abnormalities, worst grade per patient vs baseline

Baseline grade	Worst grade per patient during treatment									
	Grade 1		Grade 2		Grade 3		Grade 4		Grade 5	
	N	%	N	%	N	%	N	%	N	%
Part A - S1 (TR)										
ALT increase	G0									
	...									
	G4									
AST increase	G0									
	...									
	G4									
...	G0									
	...									
	G4									
Part B - S1 (TR)										
ALT increase	G0									
	...									
	G4									
AST increase	G0									
	...									
	G4									
...	G0									
	...									
	G4									
Part B - S2 (RT)										
ALT increase	G0									
	...									
	G4									
AST increase	G0									
	...									
	G4									
...	G0									
	...									
	G4									

Notes: Percentage is based on number of patients by study part and sequence, when applicable.

Part A, patients assigned to Sequence 1; Part B, sequence assigned randomly.

S1, Sequence 1; S2, Sequence 2; TR, test-reference; RT, reference-test.

If a low number of patients with grade  $\geq 3$  ALT or AST increased, the following table will be omitted and the information will be provided in a listing.

Table 11.4.3.4 Time course for AST and ALT

Part A		Part B		Part A+B				Total	
S1 (TR)		S1 (TR)		S2 (RT)		S1 (TR)			
N	%	N	%	N	%	N	%	N	%
Part A				Part B				Total	
				S1 (TR)				S2 (RT)	
N	Median (range)	N	Median (range)	N	Median (range)	N	Median (range)	N	Median (range)
AST (Grade $\geq 3$ )									
Onset day									
Peak day									
Recovery day									
Days to recovery									
ALT (Grade $\geq 3$ )									
Onset day									
Peak day									
Recovery day									
Days to recovery									

Part A, patients assigned to Sequence 1; Part B, sequence assigned randomly.

S1, Sequence 1; S2, Sequence 2; TR, test-reference; RT, reference-test.

## 11.5 Linear Mixed-effects Model

If applicable, to compare the incidence of grade 4 or grade 3/4 between the combination and lurbinectedin alone, a generalized linear mixed-effects model will be fit to the data with treatment (Combination or lurbinectedin alone), period and sequence as fixed effects, and patients nested in sequences as a random effect

Table 11.5.1.1 Safety comparison between combination and lurbinectedin alone†

	Combination	Lurbinectedin alone	p-value ‡
Any grade 3/4 AE			
Any grade 4 AE			
Any grade 3/4 treatment-related AE			
Any grade 4 treatment-related AE			
Any abnormality (G3-4) in laboratory value (hema, bio)			
Any abnormality (G4) in laboratory value (hema, bio)			

† A generalized mixed-effects model will be fit for each safety evaluation

‡ p-values will be provided for the comparison between treatments (combination vs. Lurbinectedin alone) or including the sequence effect if deemed necessary.

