#### 1.1.3.1 Phase I Trials

Currently, this program comprises four single-agent studies, three in solid tumors (one ongoing in Japanese patients) ([Table 1](#)) and one in acute leukemia patients, six phase Ib combination studies with gemcitabine (GEM), capecitabine, doxorubicin (DOX), cisplatin, paclitaxel with or without bevacizumab (BEV), and irinotecan in patients with selected advanced solid tumors.

The First-in-Human (FiH) study (PM1183-A-001-08) was conducted in patients with advanced and refractory solid tumors and evaluated lurbinectedin intravenously (i.v.) infused over one hour every three weeks (q3wk). Thirty-three patients were included and thirty-one patients were treated. The recommended dose (RD) was established at an equivalent dose of 4.0 mg/m^2/q3wk [\[13\]](#). Since lurbinectedin clearance was found to be unrelated to body surface area (BSA), all patients in the RD expansion cohort were treated at a flat dose (FD) of 7.0 mg q3wk (equivalent to 4 mg/m^2). However, further

linear regression showed a strong correlation between neutropenia and its severity with the systemic exposure (area under the concentration-time curve – AUC), and for this reason, lurbinectedin prescriptions are currently calculated against BSA; moreover, phase Ib trials started with a FD and were amended to use a BSA-based dose. In this study (and subsequent studies), the median terminal plasma half-life ( $T_{1/2}$ ) was around 60 hours, with a plasma clearance (CL) close to 12 L/h though large inter-individual variability exists. Urinary excretion of unaltered lurbinectedin was almost negligible regardless of dose; the mean percentage of unaltered drug recovered in urine at the recommended dose was 0.23% [13].

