### **Lurbinectedin**

Lurbinectedin will be administered as a 1-hour (-5/+20 min) i.v. infusion on Day 1 q3wk, [REDACTED]

Patients will receive a maximum of three cycles: two consecutive cycles of lurbinectedin, one cycle with and one cycle without itraconazole co-administration (in different order depending on the Sequence 1 or Sequence 2 of treatment), followed by a third cycle with lurbinectedin alone (this last cycle optional for patients with clinical benefit).

The dose of lurbinectedin when given in combination with itraconazole for the initial three patients in Part A will be 0.8 mg/m^2. Lurbinectedin dose in Part B will be based on the acceptability of the PK and safety results from the first three patients in Part A.

In cycles with lurbinectedin as single agent, lurbinectedin will be administered at 3.2 mg/m^2.

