## 7.5 DOSE REDUCTION

Patients may continue in the study treatment at a lorbinecetin reduced dose if they present any of the following:

- Grade 4 thrombocytopenia or grade 3 thrombocytopenia concomitantly with grade  $\geq 3$  bleeding.
- Two dose delays or prolonged ( $>$  one week) dose delay due to treatment-related adverse events.

- Grade  $\geq 3$  treatment related non-hematological toxicity. Exceptions are: grade  $\geq 3$  nausea and/or vomiting not optimally treated, grade 3 fatigue lasting < two days, grade 3 diarrhea lasting < one day or non-optimally treated, isolated grade 3 transient ALT/AST elevations which are rapidly reversible and not leading to subsequent delays, and non-clinically relevant isolated biochemical abnormalities.
- Grade 4 neutropenia or any grade febrile neutropenia.

Up to two dose reductions are allowed per patient. Patients who continue to experience treatment-related toxicity and/or dose delays after two dose reductions must be withdrawn from the study. Once the dose has been reduced for an individual patient, it will not be re-escalated under any circumstances.

Lurbinectedin dose reduction levels are shown in [Table 8](#).

**Table 8.** Levels of (intra-patient) lurbinectedin dose reduction in subsequent cycles in Part A and B.

Dose reduction	Lurbinectedin (q3wk) (mg/m  )	
	Lurbinectedin alone	Itraconazole co-administration cycle
1 (starting dose)	3.2	0.8
-1	2.6	0.6
-2	2.0	-

Lurbinectedin total doses in mg will be rounded to the first decimal, if necessary.  
q3wk, every three weeks.

Patients who experience any treatment-related grade 3/4 hypersensitivity and/or extravasation reactions will permanently discontinue treatment.

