In case of lurbinectedin delay ( $\leq 2$  days), itraconazole could be administered during a maximum of 14 days.

This study will consist of two parts: Part A and B. The dose of lurbinectedin when given in combination with itraconazole for the initial three patients in Part A will be  $0.8 \text{ mg/m}^2$ , and in Part B is susceptible to be adjusted properly if deemed necessary based on exposure and safety experience in Part A. The dose of lurbinectedin during Parts A and B will be  $3.2 \text{ mg/m}^2$  for all patients when administered without itraconazole. If toxicity occurs, the appropriate intra-patient dose level (DL) reductions will be implemented in the subsequent cycle.

In Part A, three patients will be enrolled to Sequence 1 (TR: Test-Reference) and will receive itraconazole with lurbinectedin in Cycle 1 followed by two consecutive cycles of lurbinectedin alone (the last cycle being optional for patients with clinical benefit according to the Investigator's criteria).

Enrollment for Part A will be sequential. Once the first patient enrolled has completed Cycle 1 and Cycle 2, the second and the third patients could be enrolled simultaneously, after the evaluation of lurbinectedin total PK parameters, and if no unacceptable or life-threatening toxicities have occurred for this first patient. However, if toxicity occurs, the

appropriate dose reductions will be implemented with the second and third patients based on the PK and safety information of first patient.

The dose of lurbinecetin when given in combination with itraconazole for the initial three patients in Part A will be 0.8 mg/m^2. However, if lurbinecetin exposure in the first patient of Part A does not allow an adequate PK assessment, the lurbinecetin dose of the following patients may be increased accordingly.

Upon exposure and safety assessments in Part A, the dose of lurbinecetin to be co-administered with itraconazole in Part B can be readjusted accordingly. This decision will be made by the Sponsor and study Investigators, and will be documented and communicated to the Independent Ethics Committee/Institutional Review Board (IEC/IRB).

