Therefore, the planned dose of lurbinecetin, when given with itraconazole for the remaining eight patients in Part B will be based on the acceptability of the PK and safety results from the first three patients in Part A. If the initial three patients do not experience adverse events (AEs) which might require a dose reduction, the dose of lurbinecetin may still be adjusted (based on the assumption of dose-proportional PK) to produce plasma lurbinecetin AUC values that are comparable to those when lurbinecetin is given in the absence of itraconazole. However, if toxicity occurs in the initial three patients in Part A, the appropriate dose-reduction of lurbinecetin will be implemented in Part B accordingly.

If the safety and PK data obtained from the three patients in Part A is deemed acceptable as defined in the protocol, Part B of this study will begin enrollment. Therefore, once Part A is completed, patients in Part B will be enrolled based on the review of the safety following completion of the first cycle of the previous patient(s), and will be randomized in a 1:1 ratio to Sequence 1 (as used in Part A) or Sequence 2 (RT: Reference-Test; lurbinecetin + itraconazole in Cycle 2).

In Part A, all patients will receive itraconazole plus lurbinecetin in Cycle 1 and lurbinecetin alone in Cycles 2 and 3 (this last cycle being optional).

In Part B, patients will be randomly assigned to the corresponding sequences:

- Sequence 1 (TR) (same used in Part A):
  - Cycle 1: Itraconazole + lurbinecetin
  - Cycle 2: Lurbinecetin alone
  - Cycle 3: Lurbinecetin alone (optional)
- Sequence 2 (RT):
  - Cycle 1: Lurbinecetin alone
  - Cycle 2: Itraconazole + lurbinecetin
  - Cycle 3: Lurbinecetin alone (optional)

Lurbinecetin will be administered to 11 evaluable patients for PK analyses and for a maximum of three cycles, while considered to be on the patient's best interest or until PD, unacceptable toxicity, intercurrent illness of sufficient magnitude to preclude safe continuation of the study, patient's refusal and/or non-compliance with study requirements, a protocol deviation with an effect on the risk/benefit ratio of the clinical

study, more than one lorbinecetin dose reduction due to AEs related to lorbinecetin (unless clear clinical benefit has been documented and always with the Sponsor's agreement) or any other reason at the physician's judgment that precludes lorbinecetin continuation.

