#### 4.1.2 *Secondary*

- To assess the effect of itraconazole on lurbinectedin unbound plasma exposure.
- To assess the effect of itraconazole on lurbinectedin major metabolites (i.e., M1 and M4).
- To assess the effect of itraconazole on the safety profile of lurbinectedin.
- To collect and store a blood sample for germline DNA extraction for future pharmacogenetic (PGt) analysis of variations on genes that may influence exposure and response (i.e., disposition, metabolism and safety) to lurbinectedin.

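### The optional safety model in SAP 11.5 has no dose or exposure term, so its p-values confound the lurbinectedin dose difference with itraconazole, and about 11 patients can barely support it

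*SAP*

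**What the plan says.** The secondary safety objective in SAP 4.1.2 is "To assess the effect of itraconazole on the safety profile of lurbinectedin". SAP 11.5 provides that, if applicable, "to compare the incidence of grade 4 or grade 3/4 between the combination and lurbinectedin alone, a generalized linear mixed-effects model" will be fitted. Treatment, period and sequence are fixed effects and patient within sequence is random. Table 11.5.1.1 has a p-value column for six outcomes: any grade 3/4 or grade 4 adverse event, the same two for treatment-related events, and any grade 3–4 or grade 4 laboratory abnormality. The section gives no criterion for when the model applies, no significance level, no analysis set and no fallback for non-convergence.

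On dose, SAP 2 sets 3.2 mg/m² "for all patients when administered without itraconazole" and 0.8 mg/m² with itraconazole for the three Part A patients. After Part A the combination dose may be moved to give "AUC values that are comparable to those when" lurbinectedin is given alone. Protocol Table 8, which covers "dose reduction in subsequent cycles in Part A and B", lists 3.2 and 0.8 mg/m² as starting doses. The primary PK endpoints are dose-normalised; event incidence is not.

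Elsewhere the safety analysis is descriptive (Protocol 9.3.2, SAP 6), and SAP 7.11, on fixed or random effects models, is marked as not applicable.

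**The concern.** Within each part, treatment and planned lurbinectedin dose change together. A coefficient labelled as combination against lurbinectedin alone then absorbs any difference in dose, and the model has no term to remove it. This matters because toxicity follows exposure: Protocol 1.1.3.1 reports that "linear regression showed a strong correlation between neutropenia and its severity with the systemic exposure". If combination-cycle exposure is lower, a table with p-values could suggest that adding itraconazole is harmless or protective. That would mislead on the secondary safety objective. If the Part B dose moves, Parts A and B contribute different dose contrasts to one coefficient.

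The adverse event shells add a second difficulty. The only columns that pool Test and Reference across groups are those for Part A+B Sequence 1. There Test is always Cycle 1, and Reference is Cycle 2 plus the optional Cycle 3. Period is therefore tied to treatment in that summary.

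**Working it through.** **The plan's own precision figure.** The only one is for PK (SAP 5.2): a 90% CI half-width of 0.389 with eight patients and a CV of 40%. Taking the log-scale SD as 0.40, t(0.95, 6 df) × 0.40 × √(2/8) = 1.943 × 0.40 × 0.5 = 0.3886, so it reproduces. (exp(±0.389) is 68% to 148%, slightly wider than the stated 70% to 147%; this has no bearing here.) No precision or power is given for safety.

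**Exposure under the starting doses.** Inputs: 0.8 and 3.2 mg/m² (Protocol 7.2); linear PK over 0.5–4.5 mg/m², and clearance reductions of about 40% (strong inhibitor, voriconazole) and 20% (moderate inhibitors) from the population model (Protocol 1.1.3.5); about 30% with aprepitant (Protocol 3.2).

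Test/Reference exposure = (0.8/3.2) × AUC ratio, with AUC ratio = 1/(1 − clearance reduction).

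| Clearance reduction | AUC ratio | Test as share of Reference |
|---|---|---|
| 20% | 1.25 | 31% |
| 30% | 1.43 | 36% |
| 40% | 1.67 | 42% |
| 50% | 2 | 50% |
| 75% | 4 | 100% |
| 80% | 5 | 125% |

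The 50%, 75% and 80% rows are assumed values that extend the range. Exposures are equal only at an AUC ratio of 4. Protocol 3.2 itself expects exposure at 0.8 mg/m² with itraconazole not to exceed that of 3.2 mg/m² alone.

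**What about 11 patients can show.** Sequences would be 3 + 4 = 7 TR and 4 RT. As a rough stand-in for the model (it ignores period), take an exact paired test at an assumed two-sided 0.05. With k discordant pairs all one way, p = 2 × 0.5^k: k = 5 gives 0.0625 and k = 6 gives 0.031. At least six discordant pairs in one direction are needed.

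Power sums the multinomial probabilities of significant outcomes, with discordance probabilities pR(1 − pT) and (1 − pR)pT and within-patient independence assumed. The illustrative Reference rate is the 69% grade 3/4 neutropenia estimate in Protocol 1.1.3.5; Test rates are assumed.

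- Test 40%, 20%, 10%: power 11%, 41%, 65%.
- Test 90%, the harmful direction: power 3.6%.
- Reference 40% (the grade 4 neutropenia rate at the recommended dose in Protocol 1.1.3.1) with Test 20% or 10%: power 4.5% or 11%.

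**Separation.** Intercept, treatment, period and sequence saturate the four sequence-by-period cells. If any cell has 0% or 100% events, the treatment estimate is not finite. The probability is 1 − Π(1 − pⁿ − (1 − p)ⁿ) over the four cells. For Reference 69% and Test 40% with 7 + 4 patients: 1 − 0.970 × 0.925 × 0.764 × 0.845 = 0.42. For Test 69%, 20% and 10% it is 0.50, 0.67 and 0.87. For Reference 40% with Test 40% and 10% it is 0.33 and 0.85.

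**The case against.** The other side has several sound points.

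- A reader might infer that the p-values measure dose and not itraconazole. The documents do not support that. The contrast is the net of a lower dose, raised exposure per mg and itraconazole's own toxicity; at an AUC ratio near 4 the first two would cancel.
- A reader might take the 4:1 contrast to hold throughout. It is settled only as the Part A starting dose. Table 8 allows it in Part B, but the dose text lets the combination dose move toward matched AUC. Matching would shrink the confounding, though it would still not compare the two at equal dose.
- The model is conditional, and SAP 11.5 names no objective. The stated safety analysis is descriptive, so one should not say that the objective rests on this table. The remaining fault is that nothing says when the condition is met.
- Eight patients is the PK comparison set. The safety set is everyone given lurbinectedin, including treated patients who are replaced, so about 11 or more. The calculations above use 11.
- The shells do show Part B Sequence 1 and Sequence 2 side by side, and SAP 11.2, 11.3.1 and 11.4 permit extra groupings if required. A period-balanced view is available to a careful reader but is not mandated.
- Doses per patient and cycle are already in Listings 13.3 and 13.17, and the PK analysis plan is a separate document that may cover exposure and safety.

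These points narrow the claim. None puts dose or exposure into the model or makes it reliably estimable.

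**Conclusion.** The point stands as confounding in an optional model. If run as written, its p-values cannot separate itraconazole from the lurbinectedin dose. At the Part A starting doses and clearance reductions of 20% to 40%, combination-cycle exposure would be 31% to 42% of Reference, so a favourable result could come from the lower dose. With 11 patients, paired-test power is 11% to 65% for drops from 69% to 40% or 10%, and the chance of separation at that Reference rate is 42% to 87%.

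These sizes rest on dose-proportional PK, on clearance reductions seen with other inhibitors, on a two-sided 0.05 level that the SAP does not state, and on illustrative event rates. The 69% is a model estimate at a baseline neutrophil count of 2.0 × 10⁹/L, the eligibility floor; the 40% comes from a higher dose.

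The conflict with SAP 7.11 needs no assumption, nor does the mismatch with the descriptive plan. The primary PK comparison is dose-normalised and is not affected.

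**What to change.** - Remove the models and the p-value column from SAP 11.5. At minimum, label them exploratory and not attributable to itraconazole at equal dose, and state the criterion for running them, the analysis set and a fallback for non-convergence.
- Show safety by treatment with the actual lurbinectedin dose by part, and put individual AUC in patient-level listings.
- Add Part B Test and Reference columns pooled over both sequences to the adverse event tables. Limit them to Cycles 1 and 2 and show Cycle 3 separately.
- Reconcile 11.5 with SAP 7.11, SAP 6 and Protocol 9.3.2.

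The cost is SAP wording, table shells and linking AUC values from the PK analysis. The downside is that no formal safety test remains. No change to dosing is proposed.
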